### **3.2 Discontinuation/Withdrawal Criteria**

#### **3.2.1. Discontinuation of Vaccination**

Discontinuation of study vaccination does not represent withdrawal from the study.

As certain data on clinical events beyond study vaccination discontinuation may be important to the study, they must be collected through the participant's last scheduled follow-up, even if the participant has discontinued study vaccination. Therefore, all participants who discontinue study vaccination prior to completion of the vaccination period, will still continue to participate in the trial.

Participants may discontinue study vaccination at any time for any reason or be dropped from the study vaccination at the discretion of the investigator should any untoward effect occur. In addition, a participant may be discontinued from study vaccination by the investigator if study vaccination is inappropriate, the trial plan is violated, or for administrative and/or other safety reasons.

A participant must be discontinued from study vaccination but continue to be monitored in the study for any of the following reasons:

- The participant requests to discontinue study vaccination.

For participants who are discontinued from study vaccination but continue to be monitored in the trial, all visits and procedures, as outlined in the trial flowchart, should be completed, except for serum collection for HPV testing at the final visit.

Participants may be allowed to begin study vaccination again if deemed medically appropriate.

### **3.2.2. Withdrawal from the Study**

A participant must be withdrawn from the study if the participant withdraws consent from the study. If a participant withdraws from the study, they will no longer receive study vaccination or be followed at scheduled protocol visits. When a subject discontinues/withdraws from participation in the trial, all applicable activities scheduled for the final trial visit should be performed except for serum collection for HPV testing at the time of discontinuation. Any adverse events which are present at the time of discontinuation/withdrawal should be followed in accordance with the safety requirements outlined in Section 3.4.2 - Assessing and Recording Adverse Events.

### **3.2.3. Lost to Follow-up**

If a subject fails to return to the clinic for a required study visit and/or if the site is unable to contact the subject, the following procedures are to be performed:

- The site must attempt to contact the subject and reschedule the missed visit. If the subject is contacted, the subject should be counselled on the importance of maintaining the protocol-specified visit schedule.
- The investigator or designee must make every effort to regain contact with the subject at each missed visit (e.g. phone calls and/or a certified letter to the subject's last known mailing address or locally equivalent methods). These contact attempts should be documented in the subject's medical record.
- Note: A subject is not considered lost to follow up until the last scheduled visit for the individual subject. The amount of missing data for the subject will be managed via the pre-specified data handling and analysis guidelines.

## **3.3 Immunogenicity Measurements**

The assay used in this study is the 9-valent HPV cLIA. The purpose of the assay is to detect antibodies to HPV VLPs types 6, 11, 16, 18, 31, 33, 45, 52, and 58, before and after vaccination with GARDASIL®9. Tests will be performed by Focus Diagnostics, Inc. (California, U.S.A) to measure HPV antibodies at baseline and evaluate the serological response after vaccination. Yeast-derived VLPs are coupled to a set of 9 distinct fluorescent Luminex microspheres. Antibody titres are determined in a multiplexed, competitive format in which known HPV type-specific, phycoerythrin-labelled, neutralising monoclonal antibodies (mAbs) compete with the subject's serum antibodies for binding to type-specific conformationally sensitive, neutralizing epitopes on the VLPs. The fluorescent signals from the bound

HPV –specific detection mAbs are inversely proportional to the subject’s neutralizing antibody titres. Results for the assay are reported as a concentration of antibody in arbitrary milli-Merck Units per millilitre (mMU/mL). The HPV 6, 11, 16, 18, 31, 33, 45, 52, and 58 cLIA is performed in a 96-well microtitre plate. A 12-point standard curve using reference serum pool from adult females immunized with 9 -vHPV vaccine, 4 controls, and 16 samples are added to the plate in duplicate. Samples are tested at a 1:4 and a 1:40 dilution. The detection antibodies followed by the VLP-microspheres for types 6, 11, 16, 18, 31, 33, 45, 52, and 58 are added to each well. The plates are sealed with foil covers and incubated for 15 to 25 hours. Following incubation, the plates are washed and then analysed on a BioPlex (Luminex) instrument. The seropositivity cutoffs for HPV types are assessed using a panel of sera from subjects that are highly likely to be HPV naïve (children), and from subjects who are likely to be seropositive. Any sample being tested for a specific HPV type with a cLIA titre lower than the cutoff corresponding to that HPV type is considered seronegative for that HPV type.

### **3.4 Safety Measurements**

#### **3.4.1 Clinical Measurements for Safety**

All subjects will be observed for at least 15 minutes after each study vaccination for any untoward effects, including allergic reactions. This observation period will be documented in the individual subject’s source documents.

Each subject will receive a vaccination diary at the Day 1, Month 2, and Month 6 study vaccination visits. In the vaccination diary, the subject will be asked to record oral temperature in the evening after each study vaccination and daily, at the same time of day, for 4 days after each study vaccination for the purpose of identifying febrile events. They will also be asked to record any injection-site reactions prompted in the vaccination diary, i.e., injection-site tenderness, swelling, or redness occurring after each study vaccination and daily for 4 days after each study vaccination (solicited injection-site reactions). In addition to injection-site reactions prompted in the vaccination diary, the subject will be asked to assess the presence of other injection-site reactions and systemic AEs starting after each study vaccination for a total of 15 days. The subject will be asked to record injection-site and systemic AEs, concomitant medications, and concomitant vaccinations on the vaccination diary.

The information on the vaccination diary should be generated only by the subject. The subject will be expected to bring the vaccination diary to the study site at the next scheduled visit. In case of hospitalization or visit to another physician, the subject should be informed to contact the investigator immediately.

The study site personnel will review the data captured in the vaccination diary with the subject or subject’s parent/legal guardian at Visit 2 through Visit 4.

All vaccination diary information will be recorded in the individual subject’s CRF. The investigator/sub-investigator will determine causality of systemic AEs recorded on the vaccination diary using the guidelines given in Section 3.4.2.4 and will classify each event as an SAE or non-serious AE. If an oral

temperature indicates a fever (defined as an oral temperature of  $\geq 37.8^{\circ}\text{C}$ ), the AE of “fever” must be documented in the individual subject’s CRF.

At the time of vaccination diary review at the next scheduled visit, subjects will be questioned regarding any new medical conditions that occurred beyond Day 15 (after dosing). The investigator/sub-investigator will determine if the medical condition is to be reported as an SAE using the reporting guidelines provided below.

### **3.4.2 Assessing and Recording Adverse Events**

An adverse event is defined as any untoward medical occurrence in a patient or clinical investigation subject administered a pharmaceutical product and which does not necessarily have to have a causal relationship with this treatment. An adverse event can therefore be any unfavourable and unintended sign (including an abnormal laboratory finding, for example), symptom, or disease temporally associated with the use of a medicinal product or protocol - specified procedure, whether or not considered related to the medicinal product or protocol-specified procedure. Any worsening (i.e., any clinically significant adverse change in frequency and/or intensity) of a pre-existing condition that is temporally associated with the use of the study vaccine, is also an adverse event.

Changes resulting from normal growth and development that do not vary significantly in frequency or severity from expected levels are not to be considered adverse events. Examples of this may include, but are not limited to, teething, typical crying in infants and children and onset of menses or menopause occurring at a physiologically appropriate time.

Adverse events may occur during the course of the use of the study vaccine during the clinical trial or within the follow-up period specified by the protocol, or prescribed in clinical practice, from overdose (whether accidental or intentional), from abuse and from withdrawal.

Adverse events may also occur in screened subjects during any pre -allocation baseline period as a result of a protocol-specified intervention or a procedure.

All adverse events will be collected from the time the consent form is signed through 14 days following the first vaccination(s) and from the time of any subsequent vaccination(s) through 14 days thereafter, and such events will be recorded at each examination on the Adverse Event case report forms/worksheets.

#### **3.4.2.1 Definition of an Overdose for This Protocol and Reporting of Overdose to the Sponsor**

In this trial, an overdose is any dose higher than 0.75 mL of vaccine in any one dose or receiving >4 doses (0.5mL each dose).

If an adverse event(s) is associated with (“results from”) the overdose of the study vaccine, the adverse event(s) is reported as a serious adverse event, even if no other seriousness criteria are met.

If a dose of study vaccine meeting the protocol definition of overdose is taken without any associated clinical symptoms or abnormal laboratory results, the overdose is reported as a non-serious Event of Clinical Interest (ECI), using the terminology “accidental or intentional overdose without adverse effect.”

All reports of overdose with and without an adverse event must be reported within 24 hours to MSD either by electronic media or paper.

#### **3.4.2.2 Reporting of Pregnancy and Lactation to MSD**

Although not considered an adverse event, it is the responsibility of the investigators or their designees to report any pregnancy in a subject (spontaneously reported to them or detected by urine or serum pregnancy test per protocol) that occurs during the trial through 1 month following the last vaccination. If a subject becomes pregnant during the trial, including subjects who never received vaccine allocation and had a positive pregnancy test at Day 1, all related information must be reported to MSD. For subjects who become pregnant with LMP prior or equal to Day 30 following the final vaccination, the pregnancy will be collected in MSD's global safety database. Furthermore, all fetal loss pregnancy outcomes (ectopic pregnancy, elective termination, spontaneous abortion, late fetal death) must be reported as a Serious Adverse Experience (Other Important Medical Event). All subjects who receive study vaccine, including discontinued subjects who agree to provide further information, must be followed to the completion/termination of the pregnancy. In addition, if the pregnancy continues to term, the outcome (health of the infant) must be reported. If a subject receives study vaccine while breastfeeding all related information, including outcome, must be reported to MSD. Infant serious adverse experiences (SAEs) for all infants born to subjects who received study vaccine must be reported to the MSD.

All pregnancy, lactation, and infant SAE events must be reported within 24 hours to MSD either by electronic media or paper. MSD contact information can be found in the Investigator Trial File Binder. Refer to Data Entry Guidelines (DEGs) for instructions for reporting these events.

#### **3.4.2.3 Immediate Reporting of Adverse Events to the Sponsor**

##### **3.4.2.3.1 Serious Adverse Events**

A serious adverse event is any adverse event occurring at any dose or during any use of the study vaccine that:

- Results in death;
- Is life threatening;
- Results in persistent or significant disability/incapacity;
- Results in or prolongs an existing inpatient hospitalization;
- Is a congenital anomaly/birth defect;
- Is a cancer;
- Is associated with an overdose;
- Is another important medical event

Refer to Table 3 for additional details regarding each of the above criteria.

Any serious adverse event, or follow up to a serious adverse event, including death due to any cause, that occurs to any subject from the time the consent is signed through 1 month following the last vaccination, whether or not related to the study vaccine, must be reported within 24 hours to MSD either

by electronic media or paper. MSD's contact information can be found in the Investigator Trial File Binder.

Additionally, any serious adverse event brought to the attention of an investigator who is a qualified physician at any time outside of the time period specified in the previous paragraph also must be reported immediately to MSD if the event is either:

- A death that resulted in the subject discontinuing the trial or
- A serious adverse event that is considered by an investigator who is a qualified physician to be vaccine related. All subjects with serious adverse events must be followed up for outcome.

#### **3.4.2.3.2 Events of Clinical Interest**

Selected non-serious and serious adverse events are also known as Events of Clinical Interest (ECI) and must be recorded as such on the Adverse Event case report forms/worksheets and reported within 24 hours to MSD either by electronic media or paper. MSD's contact information can be found in the Investigator Trial File Binder.

Events of clinical interest for this trial include:

- An overdose of study vaccine, as defined in Section 3.4.2.1- Definition of an Overdose for This Protocol and Reporting of Overdose to MSD, that is not associated with clinical symptoms or abnormal laboratory results.

#### **3.4.2.4 Evaluating Adverse Events**

An investigator who is a qualified physician will evaluate all adverse events with respect to the elements outlined in Table 3. The investigator's assessment of causality is required for each adverse event. Refer to Table 3 for instructions in evaluating adverse events.

**Table 3: Evaluating Adverse Events**

Maximum Intensity	Mild	awareness of sign or symptom, but easily tolerated (for pediatric trials, awareness of symptom, but easily tolerated)
	Moderate	discomfort enough to cause interference with usual activity (for pediatric trials, definitely acting like something is wrong)
	Severe	incapacitating with inability to work or do usual activity (for pediatric trials, extremely distressed or unable to do usual activities) Injection site redness or swelling from the day of vaccination through Day 4 post-vaccination will be evaluated by maximum size.
Seriousness	A serious adverse event (AE) is any adverse event occurring at any dose that:	
	† Results in death; or	
	† Is life threatening; or places the subject, in the view of the investigator, at immediate risk of death from the event as it occurred [Note: This does not include an adverse event that, had it occurred in a more severe form, might have caused death.]; or	
	† Results in a persistent or significant disability/incapacity (substantial disruption of one's ability to conduct normal life functions); or	
	† Results in or prolongs an existing inpatient hospitalization (hospitalization is defined as an inpatient admission, regardless of length of stay, even if the hospitalization is a precautionary measure for continued observation. (Note: Hospitalization [including hospitalization for an elective procedure] for a pre-existing condition which has not worsened does not constitute a serious adverse event.); or	
	† Is a congenital anomaly/birth defect (in offspring of subject taking the product regardless of time to diagnosis); or	
	Is a cancer; or	
	Is associated with an overdose (whether accidental or intentional). Any adverse event associated with an overdose is considered a serious adverse event. An overdose that is not associated with an adverse event is considered a non-serious event of clinical interest and must be reported within 24 hours.	
Other important medical events that may not result in death, not be life threatening, or not require hospitalization may be considered a serious adverse event when, based upon appropriate medical judgment, the event may jeopardize the subject and may require medical or surgical intervention to prevent one of the outcomes listed previously (designated above by a †).		
Duration	Record the start and stop dates of the adverse event. If less than 1 day, indicate the appropriate length of time and units	
Action taken	Did the adverse event cause the test vaccine to be discontinued?	
Relationship to test vaccine	Did the test vaccine cause the adverse event? The determination of the likelihood that the test vaccine caused the adverse event will be provided by an investigator who is a qualified physician. The investigator's signed/dated initials on the source document or worksheet that supports the causality noted on the AE form, ensures that a medically qualified assessment of causality was done. This initialed document must be retained for the required regulatory time frame. The criteria below are intended as reference guidelines to assist the investigator in assessing the likelihood of a relationship between the test vaccine and the adverse event based upon the available	

	information. The following components are to be used to assess the relationship between the test vaccine and the AE; the greater the correlation with the components and their respective elements (in number and/or intensity), the more likely the test vaccine caused the adverse event:	
	Exposure	Is there evidence that the subject was actually exposed to the test vaccine such as: reliable history, acceptable compliance assessment (e.g., diary), seroconversion or identification of vaccine virus in bodily specimen?
	Time Course	Did the AE follow in a reasonable temporal sequence from administration of the test vaccine? Is the time of onset of the AE compatible with a vaccine-induced effect?
	Likely Cause	Is the AE not reasonably explained by another etiology such as underlying disease, other drug(s)/vaccine(s), or other host or environmental factors
Relationship to test vaccine (continued)	The following components are to be used to assess the relationship between the test vaccine and the AE: (continued)	
	Dechallenge	(not applicable for vaccines)
	Rechallenge	Was the subject reexposed to the test vaccine in this trial? If yes, did the AE recur or worsen? If yes, this is a positive rechallenge. If no, this is a negative rechallenge. (Note: This criterion is not applicable if: (1) the initial AE resulted in death or permanent disability, or (2) the trial is a single-dose vaccine trial.)  NOTE: IF A RECHALLENGE IS PLANNED FOR AN ADVERSE EVENT WHICH WAS SERIOUS AND WHICH MAY HAVE BEEN CAUSED BY THE TEST VACCINE, OR IF REEXPOSURE TO THE TEST VACCINE POSES ADDITIONAL POTENTIAL SIGNIFICANT RISK TO THE SUBJECT, THEN THE RECHALLENGE MUST BE APPROVED IN ADVANCE BY THE U.S. CLINICAL MONITOR AND THE INSTITUTIONAL REVIEW BOARD/INDEPENDENT ETHICS COMMITTEE.
	Consistency with Trial Vaccine Profile	Is the clinical/pathological presentation of the AE consistent with previous knowledge regarding the test vaccine or vaccine class pharmacology or toxicology?
The assessment of relationship will be reported on the case report forms /worksheets by an investigator who is a qualified physician according to his/her best clinical judgment, including consideration of the above elements.		
Record one of the following:	Use the following criteria as guidance (not all criteria must be present to be indicative of a vaccine relationship).	

Yes, there is a reasonable possibility of vaccine relationship	There is evidence of exposure to the test vaccine. The temporal sequence of the AE onset relative to the administration of the test vaccine is reasonable. The AE is more likely explained by the test vaccine than by another cause.
No, there is not a reasonable possibility of vaccine relationship	Subject did not receive the test vaccine OR temporal sequence of the AE onset relative to administration of the test vaccine is not reasonable OR there is another obvious cause of the AE. (Also entered for a subject with overdose without an associated AE.)

#### **3.4.2.5 Sponsor Responsibility for Reporting Adverse Events and Patient/Device Events and Incidents**

All Adverse Events will be reported to regulatory authorities, IRB/IECs and investigators in accordance with all applicable global laws and regulations.

### **3.5 Statistical analysis plan**

This section outlines the statistical analysis strategy and procedures for the study. If, after the study has begun, but prior to database lock, changes are made to primary hypotheses, or the statistical methods related to those hypotheses, then the protocol will be amended (consistent with International Conference on Harmonisation [ICH] Guideline E-9). Changes to exploratory or other non-confirmatory analyses made after the protocol has been finalized, along with an explanation as to when and why they occurred, will be listed in the clinical study report (CSR) for the study. Post hoc exploratory analyses will be clearly identified in the CSR. All statistical analyses specified in this protocol will be conducted using R, version 3.0.2 (R Foundation for Statistical Computing, Vienna, Austria, 2013).

#### **3.5.1 In-house Blinding**

All subjects in this study will receive GARDASIL®9; the study is thus open-label.

#### **3.5.2 Hypothesis/Estimation**

Objectives and hypotheses of the study are stated in Section 2.1.

#### **3.5.3 Analysis Endpoints**

##### **3.5.3.1 Immunogenicity**

The immunogenicity endpoints are:

- The cLIA GMTs to HPV 6, 11, 16, 18, 31, 33, 45, 52 and 58 at 4 weeks after Dose 3.
- The cLIA seroconversion percentages to HPV 6, 11, 16, 18, 31, 33, 45, 52 and 58 by 4 weeks after Dose 3.

A subject with a cLIA titre at or above the serostatus cutoff for a given HPV type (see Section 3.3) is considered seropositive for that type. Seroconversion is defined as changing serostatus from seronegative at Day 1 to seropositive, by 4 weeks after Dose 3.

##### **3.5.3.2 Safety**

Safety assessment will focus on injection-site adverse reactions and elevated temperatures Day 1 to Day 5 post-vaccination and systemic AEs Day 1 to Day 15 post-vaccination, reported on the vaccination diary. In addition, SAEs and pregnancy will be collected from the time the ICF is signed through 1 month following the last vaccination.

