(f) If the subject has a fever (defined as an oral temperature of  $\geq 37.8^{\circ}\text{C}$ ) within the 24-hour period prior to receiving a study vaccination, the subject should not receive study vaccine, and the vaccination visit should be rescheduled until after the fever has resolved. Oral temperature will be measured prior to each vaccination

(g) Blood sample for anti-HPV measurements must be collected prior to the first study vaccination. Serum must be shipped as specified by MSD. The retention serum vial must remain at the study site until the MSD notifies the study site to ship the samples

(h) The investigator should instruct the subject to use the vaccination diary to document oral temperature in the evening after each study vaccination and daily, at the same time of day, for 4 days after each study vaccination. Additionally, injection-site and systemic adverse event(s) (AEs), concomitant

medications, and concomitant vaccinations are to be documented in the vaccination diary starting after each study vaccination for a total of 15 days, including the day of vaccination (Day 1 to Day 15).

- (i) Observe subjects for at least 15 minutes after each vaccination for immediate untoward effects. Serious adverse events (SAEs), pregnancy events, and lactation events should be reported to MSD Belgium, within 24 hours. Adverse events and SAEs will be followed for 15 days and during the whole study, respectively, after the last dose (i.e., after the third dose for subjects completing the vaccination schedule or after the last received dose in the event of the subject withdrawing).

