## **2.7 List of Safety Measurements**

Each subject will receive a vaccination diary at the Day 1, Month 2, and Month 6 study vaccination visits. In the diary, the subject will be asked to record oral temperature in the evening after each study vaccination and daily, at the same time of the day, for 4 days after each vaccination, starting at the day of vaccination, for the purpose of identifying febrile events. In addition, beginning after each study vaccination and for a total of 15 days including the day of vaccination (Day 1 to Day 15), the subject will be asked to record injection-site and systemic adverse events (AEs), concomitant medications, and concomitant vaccinations on the vaccination diary. Serious adverse events (SAEs), pregnancy information, and lactation information will also be collected as described in Section 3.4. In addition, new medical conditions not present at baseline and not reported as an AE (i.e., incident medical conditions occurring outside of a Day 1 to Day 15 period post-vaccination and not considered SAEs) will be collected throughout the study. In case of pregnancy, the pregnancy and any serious adverse experiences in study subjects and their infants must be followed to outcome. In addition, if subjects receive study vaccine while breastfeeding during the Day 1 through Month 7 period, any serious adverse experiences in the study subjects and their infants must be followed to outcome.

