**Table 6: Analysis Strategy for Safety Parameters**

Adverse Event Endpoint	Follow-Up Period		Summaries/Analyses			
	After Any Vaccination Visit		Any Time During Study	Incidence	Risk Difference and 95% CI (b)	p-Value
	Day 1 to Day 5 (a)	Day 1 to Day 15 (a)				
Clinical AE						

 
Any AE
 
Death
 
		•	•	•		

 
Injection-site adverse events (c)
 
						

 
Injection-site pain/tenderness, swelling, and redness
 
Other injection-site adverse reactions
 
Severe injection-site adverse reactions
 
Number (%) of subjects by maximum intensity rating, over all injection-site adverse reactions
 
Number (%) of subjects by maximum intensity rating, within each of the categories of injection-site adverse reactions
 
	•			•	• (d)	•
Systemic AEs						

 
Systemic AEs
 
Number (%) of subjects by maximum intensity rating, over all systemic AEs
 
		•		•	• (e)	
Temperatures						

 
Elevated temperatures (f)
 
Maximum temperatures (g)
 
	•			•	•	•

AEs of special interest						

 
• Serious AEs
 
• Serious VR AEs
 
• New medical conditions
 
		•	•	•	•	

(a) The day of vaccination is counted as Day 1.
 
(b) Defined as the difference in incidence between the comparison groups (SOT and HIV patients versus historical controls).
 
(c) For the injection-site redness and swelling 0 to 2.5 cm (0 to 1 inch) will be categorized as mild, >2.5 to 5 cm (>1 inch to 2 inches) will be categorized as moderate, and >5 cm (>2 inches) will be categorized as severe.
 
(d) Only for injection-site adverse reactions occurring in <math>\geq 1\%</math> of subjects in either group.
 
(e) Only for systemic AEs occurring in <math>\geq 1\%</math> of subjects in either group.
 
(f) Defined as maximum (over the follow-up period) temperature <math>\geq 37.8^\circ\text{C}</math>.
 
(g) Distribution of maximum temperatures over the relevant follow-up period.
 
AEs, adverse events; VR, vaccine-related.
						

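### Unsolicited injection-site reactions are collected to Day 15 after each dose, but every injection-site row in the analysis stops at Day 5

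*Combined protocol and SAP*

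**What the plan says.** **Collection.** Note (h) to the flow chart in Section 1.6 says that injection-site and systemic AEs "are to be documented in the vaccination diary starting after each study vaccination for a total of 15 days", counting the day of vaccination as Day 1. Section 2.7 gives the same Day 1 to Day 15 period. Section 3.4.1 divides local reactions into two kinds:

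- Tenderness, swelling and redness are prompted, "occurring after each study vaccination and daily for 4 days after each study vaccination (solicited injection-site reactions").
- For everything else at the injection site, the participant is asked "to assess the presence of other injection-site reactions and systemic AEs starting after each study vaccination for a total of 15 days".

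**Analysis.** Section 3.5.3.2 says the safety assessment will focus on "injection-site adverse reactions and elevated temperatures Day 1 to Day 5 post-vaccination", and on systemic AEs to Day 15. In Table 6 a single injection-site block holds the solicited reactions, the other reactions, the row "Severe injection-site adverse reactions" and two maximum-intensity rows. Its only follow-up mark is Day 1 to Day 5. Note (a) to Table 6 makes the day of vaccination Day 1. Section 3.5.5.2 also promises a summary of all AEs by vaccination visit and overall, and Table 6 has a row for any AE that runs to Day 15 and reports incidence only.

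**Two other day counts.** Section 2.7 asks for oral temperature in the evening after vaccination and daily "for 4 days after each vaccination, starting at the day of vaccination". Table 3 says: "Injection site redness or swelling from the day of vaccination through Day 4 post-vaccination will be evaluated by maximum size".

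**The concern.** Both tolerability hypotheses in Section 2.2.2 are judged on local as well as systemic reactions, and neither sets a day limit. Systemic AEs are summarised over the full 15 days for which they are collected. Unsolicited local reactions are collected for the same 15 days but summarised for five, and no reason is given.

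A reader of the final tables could not tell how many participants had an unsolicited local reaction starting after Day 5, or how severe such reactions were, although the diary holds that information.

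The day-count wording raises a smaller, separate issue. If Section 2.7 or Table 3 is read as ending on the fourth day with vaccination as Day 1, the last day of the Day 1 to 5 analysis window has no temperature or no size measurement. Section 3.5.5.2 rules out imputing missing safety data.

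**Working it through.** The plan states no figure for this point, so there is none to reproduce. The check compares windows, with the day of vaccination as Day 1 (Table 6, note a).

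**1. Collection against analysis**

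| Item | Collected | Summarised as a local reaction |
|---|---|---|
| Solicited tenderness, swelling, redness | vaccination day + 4 days = Day 1–5 (3.4.1) | Day 1–5 |
| Other injection-site reactions | Day 1–15 (1.6, 2.7, 3.4.1) | Day 1–5 |
| Severe and maximum intensity, over all local reactions | includes the other reactions, so to Day 15 | Day 1–5 |

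The windows agree for solicited reactions. For the other two rows, the days outside any injection-site summary are 15 − 5 = 10 per dose, or 10/15 = 67%. Over three doses this is 3 × 10 = 30 of 3 × 15 = 45 days.

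**2. Where a reaction starting on Day 6–15 is reported**

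- It is not a systemic AE.
- It is not a new medical condition, because Sections 2.7 and 3.5.5.3 define those as arising outside Day 1–15.
- It enters the row for any AE and the general AE summary. If serious, it also enters the serious AE rows.
- Section 3.5.5.2 defines incidence per subject. A participant with early tenderness already counts in the row for any AE, so a later local reaction does not change that row. The row has no intensity rating and no split between local and systemic events.

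**3. Possible size.** The documents give no rate of late local reactions. Assume that a share q of participants has a local reaction only after Day 5. The expected number absent from the injection-site rows is n × q, and the chance of at least one is 1 − (1 − q)^n. Planned group sizes are 100 HIV and 170 SOT patients (Section 2.5.2).

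| q (assumed) | HIV, n = 100: expected; chance of ≥ 1 | SOT, n = 170: expected; chance of ≥ 1 |
|---|---|---|
| 1% | 1.0; 63% | 1.7; 82% |
| 3% | 3.0; 95% | 5.1; 99% |
| 5% | 5.0; 99% | 8.5; >99% |

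**4. The two day counts**

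- Section 2.7, temperature only: four days beginning with the vaccination day is Day 1–4; the evening of vaccination plus four further days is Day 1–5. Sections 1.6 and 3.4.1 support the second reading.
- Table 3, size of redness and swelling: with vaccination as Day 1, Day 4 is one day short of the endpoint. If Day 4 means four days after the dose, it is Day 5 in Table 6 and there is no conflict. Section 3.5.3.2 uses the term post-vaccination with the Table 6 count, so the first reading cannot be dismissed.
- On the shorter readings, 1 of 5 analysed days (20%) lacks a measurement. For elevated temperature, defined in note (f) as a maximum over the period, that matters only if the first fever falls on Day 5.

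**The case against.** The strongest reply is that nothing is discarded. All AEs are to be summarised whatever their incidence, the row for any AE runs to Day 15, and Section 3.5.3.2 says the assessment will focus on these windows, not that it is confined to them. This stands. A reader might infer that late local reactions vanish from the tolerability result; the documents do not support that. What is missing is a local-reaction incidence and intensity summary beyond Day 5.

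A second reply is that five days is a coherent design for solicited reactions. That is also right, and limits the point to unsolicited reactions and the severity rows that include them.

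A third concerns bias. It is tempting to say that the short window favours a finding of good tolerability. The hypotheses are comparative, and note (b) to Table 6 defines the risk difference against historical controls. A common Day 1 to 5 window does not by itself favour either side, and nothing in the documents shows a different time course in these patients. No bias in that comparison is established.

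Finally, a reaction that begins by Day 5 and worsens later need not lose its severe rating. Table 3 records maximum intensity per event, and Table 6 does not say whether its window refers to onset or cuts off later intensity.

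**Conclusion.** The point holds in a narrow form, as a low-cost improvement. Unsolicited injection-site reactions starting on Day 6 to 15 are collected but have no injection-site incidence or intensity row. With the same participants in the denominator, a Day 1 to 15 within-cohort incidence can only equal or exceed the Day 1 to 5 figure; by how much cannot be found from the documents. The 67% counts calendar days and should not be read as a share of reactions, and the 1% to 5% rates above are assumptions.

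The wording in Section 2.7 and Table 3 is a separate day-count ambiguity. A reader might take it as the reason late reactions are left out, but Section 2.7's phrase concerns temperature only, Table 3's concerns size grading, and neither affects what is reported after Day 5.

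The conclusion rests on reading the Table 6 injection-site block as marked for Day 1 to 5 only. The column positions should be checked against the typeset table, but Section 3.5.3.2 states the same window in prose.

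**What to change.** 1. Keep Day 1 to 5 for the solicited reactions and for all comparisons with historical controls.
2. Add to Table 6 within-cohort incidences with 95% CI over Day 1 to 15, separately for HIV and SOT patients, for other injection-site reactions and for severe and maximum-intensity reactions. Add a footnote that redness and swelling are graded by size only within the solicited window, so that the mixed basis of grading is visible. State whether a reaction is assigned to a window by its day of onset.
3. Reconcile Section 2.7 (temperature) and Table 3 (size grading) with Section 3.4.1 and the Day 1 to 5 window of Table 6, using one day-count convention throughout, so that Day 5 temperature and size are not lost.

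The cost is a few extra table rows from data already collected and two wording corrections, with no added visits. The reported local-reaction incidence may be slightly higher. The added rows combine prompted capture to Day 5 with unprompted capture afterwards, so they should be presented as descriptive.
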